2.6.3 Dose Increase (Part 4)

The Cohort 11 starting dose is 175 mg/m²/day for 28 days. If the patient's response is inadequate after at least one post-baseline assessment and they are not experiencing toxicities at this dose level, the Investigator may increase the dose to 200 mg/m²/day after discussion with the Sponsor.

2.6.4 Management of Neutropenia (Part 4)

Patients in Cohort 11 of Part 4 may receive supportive care for bone marrow and/or gastrointestinal adverse events (e.g., with growth factors, antidiarrheals, antiemetics) and prophylaxis following institution's standard of care.

- A short-acting GCSF should be given daily if the ANC drops below 1,000/mm³. CBCs should be done twice weekly and TK216 dosing can continue.
- GCSF should be continued until ANC is above 2,000/mm³.
- If ANC ≤ 500/mm³ TK216 should be held until ANC > 1000/mm³.

3. Patient Eligibility

3.1 Inclusion criteria

Patients who meet the following inclusion criteria will be eligible to participate in this study:

1. Willing and able to provide written IRB/IEC-approved Informed Consent. For patients < 18 years of age, their parents or legal guardians must sign a written informed consent. Assent, when appropriate, will be obtained according to institutional guidelines.
2. Have histologically or cytologically confirmed diagnosis of Ewing sarcoma (including ESFT) with relapsed or refractory disease
 - a. who have failed standard therapy and for whom no known curative therapy exists (For Parts 1-3), OR
 - b. patients with metastatic disease who had standard chemotherapy at the time of diagnosis (Part 4)

(NOTE: as of Protocol version 7, pathology reports and slides or blocks should be available for review or additional testing. If not available, site must discuss with Sponsor.)

3. Measurable disease according to RECIST version 1.1. Measurable disease can be verified from a previously documented CT scan or MRI as long as no anti-cancer treatments have been administered in the interim.
4. Must have a central venous catheter in place prior to initiating infusion of study drug.
5. Prior cancer therapy:
 - a. Patients may have received any number of prior therapy regimens. In the Investigator's opinion, patients must have tolerated prior cytotoxic therapies well and have adequate bone marrow reserve. At the time of treatment initiation, at least 3 weeks must have elapsed after prior cytotoxic chemotherapy. At least 7 days must have elapsed since completion of any prior non-cytotoxic cancer therapy and any associated AEs must have resolved.(For Parts 1-3) OR
 - b. Patients may have received no more than five prior systemic regimens. At the time of treatment initiation, at least 3 weeks must have elapsed since prior cytotoxic chemotherapy. At least 7 days must have elapsed since completion of any prior non-cytotoxic cancer therapy. (For Part 4)
6. Prior radiotherapy is allowed
 - a. If ≥ 2 weeks have elapsed for local palliative XRT (small port); ≥ 6 months must have elapsed if prior total body irradiation, craniospinal XRT or if $> 50\%$ radiation of the pelvis; ≥ 6 weeks must have elapsed if other substantial bone marrow radiation. Patients who have received brain irradiation must have completed whole brain radiotherapy and/or gamma knife at least 4 weeks prior to enrollment (Parts 1-3) OR
 - b. If ≥ 4 weeks has elapsed for radiation therapy (RT); ≥ 6 months must have elapsed if prior total body irradiation, craniospinal RT or if $> 50\%$ radiation of the pelvis; ≥ 6 weeks must have elapsed if other substantial bone marrow radiation. Patients who have received brain irradiation must have completed whole brain radiotherapy and/or gamma knife at least 4 weeks prior to enrollment. (Part 4)
7. Stem Cell Transplant or Rescue without TBI: No evidence of active graft vs. host disease and ≥ 3 months must have elapsed since transplant.

8. Patients with controlled asymptomatic CNS involvement are allowed (see Concomitant Medications). Patients not requiring steroids or requiring steroids at stable dose (≤ 4 mg/day dexamethasone or equivalent) for at least 2 weeks are eligible.
9. Resolution of all acute toxic effects (excluding alopecia) of any prior anti-cancer therapy to NCI CTCAE (Version 4.03) Grade ≤ 1 or to the baseline laboratory values as defined in the table below.
10. Eastern Cooperative Oncology Group (ECOG) performance status (PS) ≤ 2 in patients ≥ 17 years old; or Karnofsky/Lansky > 50 in patients ≤ 16 years old.
11. Age
 - a. Patients age ≥ 18 years old (Cohort 1)
 - b. Patients must be ≥ 12 years old (Cohorts 2-5)
 - c. Patients must be ≥ 10 years old (Cohorts 6-10)
 - d. Patients must be ≥ 8 years old (Cohort 11)
12. Life expectancy of at least 3 months.

13. Baseline laboratory values fulfilling the following requirements:

Absolute Neutrophil Count (ANC)	$\geq 1000/\text{mm}^3$ ($\geq 1.0 \times 10^9/\text{L}$)
Platelets (PLT)	$\geq 100,000/\text{mm}^3$ ($\geq 100 \times 10^9/\text{L}$) (transfusion independent, defined as not receiving platelet transfusions within a 7 day period prior to screening)
Hemoglobin	$> 9.0 \text{ g/dL}$ (transfusions are allowed)
Serum Creatinine or Creatinine Clearance	$\leq 1.5 \times \text{ULN}$ $> 60 \text{ mL/min}$
Total Serum Bilirubin	$\leq 1.5 \times \text{ULN}$
Liver Transaminases (AST/ALT)	$\leq 2.5 \times \text{ULN}$; $\leq 5 \times \text{ULN}$ if liver metastases are present
Alkaline Phosphatase (ALP)	$\leq 2.5 \times \text{ULN}$; $\leq 5 \times \text{ULN}$ if liver and/or bone metastases are present
Serum calcium and potassium	Normal or \leq CTCAE Grade 1 with or without supplementation.
Pregnancy test if female of child-bearing potential	Negative within 7 days of starting treatment

AST/ALT = aspartate aminotransferase/alanine aminotransferase, ULN = upper limit of normal
 
Growth factor(s): Growth factors that support platelet or white cell number or function must not have been administered within the 7 days prior to screening.
	

14. Cardiac ejection fraction $\geq 50\%$ or shortening fraction $\geq 28\%$.
15. Females of child-bearing potential must have a negative pregnancy test during screening and be neither breastfeeding nor intending to become pregnant during study participation. Females of childbearing potential must agree to avoid pregnancy during the study and commit to abstinence from heterosexual intercourse or agree to use two methods of birth control (one highly effective method and one additional effective method) at least 4 weeks before the start of protocol therapy, for the duration of study participation, and for 6 months after the last dose of TK216
16. Males with partner(s) of childbearing potential must take appropriate precautions to avoid fathering a child from the screening period until 90 days after receiving the last dose of TK216. They must commit to abstinence from heterosexual intercourse or agree to use appropriate barrier contraception.
17. Prior to enrollment of females or males of reproductive potential, the investigator must document confirmation of the patient's understanding of the possible teratogenic effects of TK216.
18. Willingness and ability to comply with scheduled visits, treatment plan, laboratory tests and other study procedures.
19. If the patient is to receive vincristine, no contraindication to vincristine administration.

3.2 Exclusion criteria

Patients will not be enrolled if they meet any of the following exclusion criteria:

1. Current participation in another therapeutic clinical trial.
2. Symptomatic brain metastases.
3. History of previous cancer (non ES), except squamous cell or basal-cell carcinoma of the skin or any in situ carcinoma that has been completely resected, which required therapy within the previous 3 years.
4. Incomplete recovery from any surgery (other than central venous catheter or port placement) prior to treatment.
5. Any of the following in the past 6 months: symptomatic congestive heart failure, cerebrovascular accident or transient ischemic attack, pulmonary embolism, deep vein thrombosis, symptomatic bradycardia, requirement for anti-arrhythmic medication.
6. History of prolonged QTc interval (e.g., repeated demonstration of a QTc interval > 450 milliseconds, unless associated with the use of medications known to prolong the QTc interval).
 - (NOTE: for Part 4 repeated demonstration of a QTc interval > 470 milliseconds)
7. History of additional risk factors for torsade de pointes (e.g., heart failure, family history of long QT syndrome).
8. Use of concomitant medications that increase or possibly increase the risk to prolong the QTc interval and/or induce torsades de pointes ventricular arrhythmia.
9. Females who are breastfeeding/lactating.
10. Known active infections (e.g., bacterial, fungal, viral including hepatitis and HIV positivity).
11. Other severe acute or chronic medical or psychiatric condition or laboratory abnormality that may increase the risk associated with study participation or study drug administration or may interfere with the interpretation of study results and, in the judgment of the Investigator, would make the patient inappropriate for entry into this study or compromise protocol objectives in the opinion of the Investigator and/or the Sponsor.

4. Study Plan

4.1 Study assessments

4.1.1 Physical examination

A complete physical examination will include the following: HEENT (head, ears, eyes, nose and throat), chest, lungs, heart, lymph nodes, abdomen, skin, musculoskeletal and neurological systems. Symptom-driven physical exams will be done as needed, based on observed adverse events.

4.1.2 Height and weight

Height and weight will be measured during screening. Weight only will be measured at subsequent visits. For pediatric patients, height should be measured periodically as determined by the Investigator

4.1.3 Electrocardiogram

An electrocardiogram (ECG) will be obtained using a 12-lead electrocardiograph will be done during the screening period to determine cardiac function. Each ECG is to be evaluated by the study

investigator for the presence of abnormalities at the time the ECG is recorded. The evaluating physician is to write his/her diagnosis on the ECG recording and sign and date. In some cases, it may be useful to repeat abnormal ECG's to rule out improper lead placement as contributing to the ECG abnormality.

4.1.4 **Vital signs**

Vital signs will include:

- blood pressure, respiratory rate, heart rate (with the patient in the sitting position following an approximate 5-minute rest); two measurements of blood pressure will be taken at each determination, 1 to 5 minutes apart.
- temperature (°C)

4.1.5 **Clinical laboratory tests**

All screening clinical laboratory test results are to be reviewed and assessed by the investigator, or designee, prior to study enrollment. Any screening laboratory result that is required for eligibility that is outside the reference range as allowed by entry criteria may be repeated, as deemed necessary by the Principal Investigator. If any repeat screening values continue to be outside the reference range, the patient will be excluded from the study, unless there is agreement between the sponsor and investigator that the laboratory deviation is not clinically significant. After enrollment into the study, the CBC, serum electrolytes, BUN, creatinine, liver function tests and urinalysis are to be reviewed and assessed for safety prior to drug administration on Day 1 of each treatment cycle.

Blood samples for the following tests will be collected:

- Hematology: complete blood count (CBC) including WBC with differential (neutrophils, lymphocytes, monocytes, eosinophils, basophils) RBC, hemoglobin, hematocrit, and platelet count.
- Clinical chemistry: serum sodium, potassium, chloride, bicarbonate, calcium, magnesium, BUN, creatinine, eGFR, uric acid, total bilirubin, direct (conjugated) bilirubin, indirect (unconjugated) bilirubin (calculated), alanine transaminase (ALT), aspartate transaminase (AST), gamma-glutamyl transpeptidase (GGT), alkaline phosphatase, lactate dehydrogenase (LDH), amylase, lipase, triglycerides, total cholesterol, inorganic phosphate, total protein, albumin, creatine phosphokinase (CPK), glucose.
- Coagulation: prothrombin time (PT), and activated partial thromboplastin time (APTT). An international normalized ratio (INR) may be assessed only if the PT assessment is unavailable.

Urine will be collected for the following tests:

- Urinalysis: color, protein, glucose, bilirubin, urobilinogen, ketones, blood, pH, specific gravity, and leukocytes.

4.1.6 **Other Assessments**

4.1.6.1 **Urine pregnancy test**

Urine pregnancy tests will be conducted for all females of child bearing potential.

4.1.6.2 **Demographics**

Information regarding the patient's gender, age, and racial or ethnic origin will be collected.

4.1.6.3 **Palliative Radiation Therapy (Part 4)**

Patients may rapidly develop tumor-related symptoms even in the face of stable or minimally progressive disease. Therefore, as of Protocol version 7.0, palliative local radiation therapy may be allowed if the following criteria are met:

1. Treatment is required for a symptomatic, non-target lesion(s) (example: pain due to compression of nerve in a closed space).
2. Planned radiation therapy is focal and the field does not involve the treatment of target lesion(s) directly or indirectly by an inability to fully shield adjacent target lesions from any radiation effect.
3. There is a reasonable possibility that the patient will benefit from additional systemic therapy with TK216.
4. Approval for this treatment has been granted by Oncternal.

4.1.6.4 **Medical History**

The patient's medical history will be taken with particular attention to questions related to 1) a thorough review of body systems including any past or current conditions; 2) previous and current pharmacotherapy or chronic use of any medication within 14 days prior to screening; and 3) history of allergies or hypersensitivity to drugs.

4.1.6.5 **Performance status**

The ECOG performance status (in patients ≥ 17 years old) or the Karnofsky /Lansky status (in patients ≤ 16 years old) will be assessed at Screening and at the beginning of each cycle.

4.1.6.6 **Tumor assessments**

For the Part 1 dose escalation segment, tumor assessments will be performed from evaluation of a CT or an MRI scan obtained within 10 days of beginning Cycle 1 at and after completing the infusions of Cycles 2, 4, 6, etc (i.e., every 6 weeks).

For the Part 2 schedule escalation segment, tumor assessments will be performed soon after the end of the infusion during each even-numbered cycle but prior to initiating the infusion for the next cycle.

For the Part 3 expansion segment, the scan schedule will be at the end of every even-numbered cycle's rest period, and prior to starting the next infusion. The same methodology should be used for all assessments throughout the study. Assessments will be done using RECIST, version 1.1. Tumor

assessments will continue to be done after the patient discontinues from the study, until the criteria for progressive disease have been met, or the patient begins another cancer therapy, or withdraws consent.

For the Part 4 dose and schedule evaluation segment, tumor assessments will be performed from evaluation of a CT (chest/abdomen/pelvis) or an MRI scan obtained within 10 days of beginning Cycle 1 and approximately every 8 weeks thereafter (e.g. after completing the infusions of Cycles 2, 4, 6, etc).

4.1.7 **Adverse events**

An adverse event (AE) is any untoward medical occurrence in a patient administered a study drug, and that does not necessarily have a causal relationship with the study drug. (An AE can be any unfavorable and unintended sign or symptom, or disease temporally associated with the use of a study drug, whether or not related to the study drug.) Adverse events include any symptom, physical sign, syndrome or disease which either occurs during the study, having been absent at baseline, or, if present at baseline, appears to worsen during the course of a clinical trial, after starting treatment, whether considered treatment related or not.

Events involving adverse drug reactions, illnesses with onset during the study, or exacerbations of pre-existing illnesses should be recorded. Exacerbation of a pre-existing illness is defined as a manifestation (sign or symptom) of the illness that indicates a significant increase in the severity of the illness as compared to the severity noted at the start of the study. It may include a worsening or increase in severity of signs or symptoms of the illness, increase in the frequency of signs and symptoms of an intermittent illness, or the appearance of a new manifestation/complication.

Exacerbation of a pre-existing illness should be considered when a patient requires new or additional concomitant therapy for the treatment of that illness during the study. Lack of, or insufficient clinical response, benefit, efficacy, therapeutic effect, or pharmacologic action, should not be recorded as an adverse event. The investigator must make the distinction between exacerbation of a pre-existing illness and lack of therapeutic effect.

For all adverse events, the investigator must pursue and obtain information adequate to determine both the outcome of the adverse event and to assess whether it meets the criteria for classification as a serious adverse event requiring immediate notification to the sponsor or its designated representative (see Appendix 1). For all adverse events, the investigator is required to obtain sufficient information to assess the causality of the adverse event (i.e., study drug or other illness).

Follow-up of the adverse event, after study drug has been discontinued, is required if the adverse event or its sequelae persist. Follow-up of all adverse events is required until the event or its sequelae resolve or stabilize at a level acceptable to the investigator and the sponsor or its designated representative.

Adverse events may be volunteered spontaneously by the patient, or be discovered as a result of general questioning by the investigator or by physical examination or laboratory tests. Patients will be continuously monitored for adverse events (AEs) during the study. At each visit during the study or at each telephone contact after the first dose, patients will be asked to specifically describe any signs, symptoms, or AEs occurring since the previous visit. Questions will be phrased so that they do not "lead" the patient into giving information that is not valid. All adverse events regardless of treatment group or suspected causal relationship to study drug will be recorded in source documentation and on the adverse event page(s) of the case report form (CRF).

Conditions that the patient experienced before treatment with study drug (Pre-dose symptoms) and any new signs, symptoms, or AEs that occur since starting treatment with study drug (regardless of causality) are to be assessed and recorded. Pre-dose baseline assessments must be performed prior to treatment with TK216. Any baseline symptoms or adverse events noted prior to treatment with TK216 should be recorded as part of the Medical History. The assessment and recording of each symptom or AE must also be described by its duration (start date, time and duration), its severity (mild, moderate, severe, very severe), its relationship to the study medication (unrelated, unlikely or possibly related), whether it influenced the course of the study medication, and whether it required specific therapy.

The severity of signs, symptoms, or AEs is to be determined by using the NCI Common Terminology Criteria for Adverse Events (CTCAE) v 4.03. If a sign, symptom or AE is not included in the toxicity severity grading scale, the intensity of the event will be graded as shown below.

- **mild (grade 1):** Symptoms causing no or minimal interference with usual social and functional activities. Symptoms are usually transient and require no special treatment.
- **moderate (grade 2):** Symptoms causing greater than minimal interference with usual social and functional activities. Symptoms are usually ameliorated by simple therapeutic measures
- **severe (grade 3):** Symptoms causing inability to perform usual social and functional activities. Symptoms traditionally require systemic drug therapy or other treatment
- **very severe (grade 4, life-threatening):** Symptoms causing inability to perform basic self-care functions or require medical or operative intervention to prevent permanent impairment, persistent disability, or death.
- **death related to AE (grade 5)**

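### Section 4.1.5 lets sponsor and investigator enrol patients who still fail laboratory limits that inclusion criterion 13 states without exception, with no bound and no recording rule

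*Combined protocol and SAP*

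**What the plan says.** Section 3.1 makes the inclusion criteria the test of eligibility: "Patients who meet the following inclusion criteria will be eligible to participate in this study". Criterion 13 then requires "Baseline laboratory values fulfilling the following requirements" and lists the limits: ANC at least 1,000/mm³, platelets at least 100,000/mm³, hemoglobin above 9.0 g/dL, total bilirubin up to 1.5 x ULN, transaminases up to 2.5 x ULN (5 x ULN with liver metastases), and others. It contains no exception by agreement.

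Section 4.1.5 (Clinical laboratory tests) deals with screening results that fail. It first allows a repeat: "Any screening laboratory result that is required for eligibility that is outside the reference range as allowed by entry criteria may be repeated", as the investigator judges necessary. It continues: "If any repeat screening values continue to be outside the reference range", the patient is to be "excluded from the study, unless there is agreement between the sponsor and investigator that the laboratory deviation is not clinically significant".

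**The concern.** The two sections give different answers for the same patient. If a repeat value still misses a criterion 13 limit, section 3.1 makes the patient ineligible. Section 4.1.5 allows enrolment if two parties agree that the deviation does not matter clinically. A site following section 3.1 and a site following section 4.1.5 can both claim to have followed the protocol.

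The limits concerned are safety entry limits, and some of the same measurements define the Part 1 and Part 2 endpoint. In Tables 1 and 2 the neutrophil and platelet DLTs are absolute counts, so a patient admitted with a low count starts closer to a DLT. Both tables also have a special transaminase rule for patients with liver metastases and baseline values of 2.5 to 5 x ULN. Its upper end matches the criterion 13 ceiling, so a patient waived in above 5 x ULN is not covered by it. Undocumented waivers would make the DLT data harder to interpret, and the study report could not show how many patients fell outside the stated population.

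**Working it through.** The main check is a comparison of text.

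1. **Which results does section 4.1.5 cover?** Its first sentence is confined to results required for eligibility, and it describes the range as the one the entry criteria allow. The exclusion sentence concerns repeat values that continue to be outside that range. In context, the range is the set of criterion 13 limits.
2. **Does the exclusion sentence conflict with criterion 13?** Criterion 13 admits some abnormal values. Calcium and potassium, for example, may be up to "CTCAE Grade 1 with or without supplementation", and liver tests may be multiples of ULN. Transaminases of 2 x ULN are inside the allowed range, so they trigger neither a repeat nor an exclusion. The exclusion sentence omits the qualifier that the first sentence carries. That is loose wording, not a contradiction.
3. **Does the exception conflict with criterion 13?** Yes. The qualifier that resolves step 2 also makes the exception apply to the criterion 13 limits themselves. Criterion 13 has no matching exception.
4. **Is an exception usually written into the criterion?** Criterion 2 does this: where pathology material is unavailable, its note tells the site to discuss with the sponsor. Criterion 13 has no such note.
5. **Is there a waiver for later cycles?** The Day 1 conditions for further cycles (sections 2.2, 2.3 and 4.2.4.1) have none. They require ANC of at least 1,000/mm³, the same value as criterion 13. A patient waived into Cycle 1 with a lower ANC would be barred from Cycle 2 at that same count. For hemoglobin (8.0 gm/dL) and platelets (50,000/mm³) the later-cycle limits are below the entry limits, so this happens only if the waived value is below those too.

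The possible size of the effect can be illustrated with the escalation table in section 9.3.

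- *The plan's own figures.* Escalation follows 0 DLTs in 3 patients, or 1 in 3 followed by 0 in the next 3. With a common DLT probability p, P = (1−p)³ + 3p(1−p)²·(1−p)³.
  - p = 0.2: 0.512 + 0.384 × 0.512 = 0.709 (table: 0.71).
  - p = 0.3: 0.343 + 0.441 × 0.343 = 0.494 (table: 0.49).
- *One waived patient among the first three.* Assume that this patient has DLT probability q, that all others have 0.2, and that outcomes are independent.
  - P(0 of 3) = (1−q) × 0.64.
  - P(1 of 3) = q × 0.64 + (1−q) × 0.32.
  - P(escalate) = P(0 of 3) + P(1 of 3) × 0.512.
  - q = 0.3: 0.448 + (0.192 + 0.224) × 0.512 = 0.448 + 0.213 = 0.661.
  - q = 0.4: 0.384 + (0.256 + 0.192) × 0.512 = 0.384 + 0.229 = 0.613.
  - q = 0.5: 0.320 + (0.320 + 0.160) × 0.512 = 0.320 + 0.246 = 0.566.

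The fall from 0.709 is thus about 0.05, 0.10 or 0.14 for these assumed values. The calculation does not apply to Part 4, which has no DLT-based escalation.

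**The case against.** The strongest reply is that the clause is narrow and other protections remain. Exclusion is the default. A waiver can follow only a failed repeat, and the sponsor cannot grant it alone because the investigator must agree. The agreed test is lack of clinical significance, which a patient with clearly poor marrow or liver function should not pass. Criterion 5a separately requires adequate marrow reserve in Parts 1 to 3, criterion 15 requires a negative pregnancy test, and exclusion 11 bars severe laboratory abnormalities that may raise risk. Section 4.1.5 also requires safety review of laboratory results before dosing on Day 1 of each cycle.

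All of this stands, and it rules out three stronger readings that a reader might infer:

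- *That the laboratory criteria do not bind at all.* They bind by default, and the exception needs two parties.
- *That the reference-range wording excludes patients whom criterion 13 admits.* The preceding sentence ties the range to the entry criteria.
- *That the chance of escalation could fall from 0.71 to 0.49.* That compares a whole cohort at 0.2 with a whole cohort at 0.3. One waived patient at 0.3 gives about 0.66.

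The reply does not remove the conflict. The marrow-reserve condition and exclusion 11 rest on judgment and set no numeric limit. Criterion 5b, for Part 4, omits the marrow-reserve condition. Parties who have already agreed that a deviation is not clinically significant are unlikely to invoke exclusion 11 for the same value.

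**Conclusion.** The point holds as a conflict between two passages. Section 4.1.5 permits an exception to limits that criterion 13 states unconditionally, and it gives no list of waivable limits, no bound and no recording rule.

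Stated alpha, power and sample size do not change. The effect is on who may be enrolled. On the assumptions above, one waived patient at 0.3 lowers the chance of escalation by about 0.05. The documents support no estimate of how often waivers would occur or how much they would raise toxicity, so this shows sensitivity and is not a forecast.

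The correction is worth making because it is cheap and concerns safety entry limits in very small cohorts. Which laboratory limit is clinically right is not addressed here.

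**What to change.** In the exclusion sentence of section 4.1.5, replace the mention of the reference range with the limits in inclusion criterion 13. Delete the clause that allows enrolment by agreement between sponsor and investigator. Keep the allowance to repeat a screening test.

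If the sponsor wants to keep an exception, state it in criterion 13 itself. Say which limits it covers and how far each may be exceeded, and require each use to be recorded. Section 4.1.5 should then simply refer to criterion 13.

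The cost is a one-sentence amendment and a few screen failures that would otherwise have been waived.
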